Research staff at the University of Michigan will maintain the website on their computer servers. [name] and her staff will finalize content and develop specifications of the website for dedicated use with the proposed protocol, beta-test the specifications, monitor step-count data during the intervention phase, maintain the Web-based applications for the intervention, and provide data from the website for analyses.

The specific items involved with developing, testing, and maintaining the website include:

- Procurring, managing and securing database and Web servers, system-level software and site/user licensing required to run the system.
- Ongoing management and maintenance of the system and system security throughout the study.
- Performing website modifications for automated weekly step-count feedback, and educational and motivational messages.
- Designing website so that subjects who are current oxygen users or active smokers will receive tailored messages about oxygen use during exercise or smoking cessation.
- Beta testing website prior to launch and routine regular maintenance.
- Providing back-up of study data. This task also includes automated backup software and scheduling, as well as obtaining and securely storing physical backup media.
- Providing study staff access to the study data systems as needed for study implementation.
- Capturing, maintaining, and securing delivery of step-count data for analysis.
- Capturing and reporting data on frequency of website use. Each time a participant logs in, or uses a link, an automated digital log entry occurs.

There is no other website currently available that has all the unique components offered by WEB (feedback, individualized goals, and educational content and motivational messages).

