### **Additional Analyses**

Additional analyses will be conducted with repeated measures ANOVA using all time points--baseline, 3, 6, and 12 months assessments of 6MWT distance--to explore the effect of the interaction between treatment and time (treatment\*time), as well as the between-subject group treatment effect (intervention versus control) and the within-subject effect (repeated over time) on 6MWT distance. We will use a mixed model (PROC MIXED in SAS) to perform the repeated measures ANOVA. We will examine both compound symmetry and AR(1) correlation structures. Models will have 6MWT distance at each time point as the dependent variable, and treatment,

time, and treatment-time as independent variables. Models will also have study site and any unbalanced baseline subject characteristics as covariates. Similarly, additional analyses will be conducted with repeated measures ANOVA using all time points--baseline, 3, 6, 9, and 12 months assessments of the secondary outcomes--to explore the effect of the interaction between treatment and time (treatment-time), as well as the between-subject group treatment effect (intervention versus control) and the within-subject effect (repeated over time) on SGRQ-TS, dyspnea score, CRP and IL-6 levels, and daily step count. We will use a mixed model (PROC MIXED in SAS) to perform the repeated measures ANOVA. Models will have the secondary outcome at each time point as the dependent variable, and treatment, time, and treatment-time as independent variables. Models will also have study site and any unbalanced baseline subject characteristics as covariates.

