As outlined in our Conceptual Model, we will also explore whether increases in PA (6MWT distance and daily step counts) result in decreases in levels of systemic inflammation and risk of AEs, regardless of treatment arm. Models, adjusting for baseline 6MWT distance or step counts, will examine whether increases in PA independently predict decreases in inflammatory biomarkers and decreased risk of AEs and COPD-related hospitalizations. We will use linear regression models with change in 6MWT distance as the independent variable, and change in IL-6 and CRP as dependent variables. A multivariate regression analysis (PROC GENMOD) will be conducted with number of AEs (or COPD-related hospitalizations) as the dependent variable, and change in daily step count and baseline daily step count as independent variables. Models will account for potential confounders such as study site, season of enrollment, age, gender, comorbid medical conditions, FEV1 % predicted, BMI, and history of prior AEs. We believe we will show that increases in 6MWT and daily step count, regardless of treatment arm, independently predict decreases in CRP and IL-6, and decreases in the risk of AEs and COPD-related hospitalizations. These exploratory models have the potential to provide significant insight into the mechanisms of the beneficial impact of walking and PA on systemic inflammation and COPD-related morbidity. The results of these exploratory analyses will provide estimates for sample size calculations for future research proposals.

(d) Discuss potential problems and limitations of the proposed methods and/or procedures and possible alternative procedures to achieve the specific aims.

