Like most clinical trials, the study may face recruitment challenges. We believe that we have carefully examined the number of Veterans with COPD and Internet access and we have an accurate assessment of the number of potential participants eligible for the trial. We acknowledge that there is no attention control group. However, the study is designed to compare the WEB intervention to usual care. Providing attention and social support are critical components of the exercise intervention under study so it would be inappropriate to control for them. An alternative control group could be pulmonary rehabilitation (PR). However, an equivalence trial comparing a program like WEB to PR is a different question than the one we are proposing which is to study the efficacy of WEB. We believe that PR would have greater positive effects on 6MWT distance than WEB. In fact, participation in a PR program within the previous 3 months is an exclusion criterion for the proposed study. Although referral to PR is recommended for the treatment of COPD, the reality is that PR is available for only a small fraction of patients with COPD. We choose counseling, reinforced with written instructions, as the control group to most pragmatically mirror usual care.

We acknowledge that the pedometer captures ambulation, but does not record upper extremity exercise or total PA. However, total walking step count has been shown to be closely related to overall daily activity in persons with COPD, and lower extremity exercise is the most effective and best-validated portion of PR programs (24,27,42,43). Furthermore, the pedometer does not provide information about the intensity of the walking performed. However, the literature and our preliminary data suggest that all forms of walking are beneficial in COPD, whether walking as part of functional community mobility or walking as part of sustained cardiovascular exercise. There may also be selection bias of subjects who are less sick and interested in an exercise research study. In sum, the proposed study has the potential to transform current clinical management of COPD and advance our understanding of how to promote PA in persons with COPD.

(e) If humans or animals are to be studied, power analysis needs to be used to justify the number to be studied. Justify the species of animal to be used. If cell lines or tissue specimens are used, discuss the source of the material.

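### The exploratory mechanism models pool both arms and name no treatment-arm term, so part of any non-walking effect of WEB would be attributed to increased walking

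*Combined protocol and SAP*

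**What the plan says.** Additional Analyses sets out exploratory models intended to show whether increases in physical activity "result in decreases in levels of systemic inflammation and risk of AEs, regardless of treatment arm". There are two families:

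- **Biomarkers:** "We will use linear regression models with change in 6MWT distance as the independent variable, and change in IL-6 and CRP as dependent variables".
- **Exacerbations and COPD-related hospitalizations:** a PROC GENMOD count model with "change in daily step count and baseline daily step count as independent variables".

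On adjustment, the section says: "Models will account for potential confounders such as study site, season of enrollment, age, gender, comorbid medical conditions", and continues with FEV1 % predicted, BMI and prior exacerbations. It also adjusts for baseline 6MWT distance or step count. Treatment arm does not appear as predictor, covariate or stratum. By contrast, the repeated-measures models in the same section have "treatment, time, and treatment-time as independent variables", and the secondary count model in the statistics section has treatment group as its main predictor.

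The section expects walking gains to be independent predictors of benefit. It adds: "These exploratory models have the potential to provide significant insight into the mechanisms of the beneficial impact of walking and PA", and says the results will supply estimates for sizing future studies.

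**The concern.** By the plan's own account, arm can act on both sides of these regressions.

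- **On the exposure:** WEB is designed to increase 6MWT distance and daily steps.
- **On the outcome, by routes other than walking:** WEB participants receive online disease-management education and an online community (Background), and a staff call every Monday with the step goal (Pedometer and Internet-mediated walking program). Under the usual-care description, the next staff contact after randomization is the 3-month visit. The limitations discussion, item (d), acknowledges that there is no attention control and says: "Providing attention and social support are critical components of the exercise intervention under study".
- **On ascertainment:** exacerbation assessment starts from what participants report to staff. Weekly contact in one arm could change reporting in that arm, and the direction of that effect cannot be assumed.

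Arm is then a common cause of walking change and outcome. A slope estimated without it mixes the association of walking with whatever else WEB does. The risk is that a mechanism paper, and the sample sizes of later studies, rest on a walking coefficient that partly reflects education, attention or reporting.

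**Working it through.** **1. The plan's own figure.** Inputs from Power Calculation: difference 54 m, SD 100 m, power 80%, alpha 0.05 (two-sided assumed).

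- n per arm = 2(1.960 + 0.842)² × (100/54)² = 53.8, so 54 by the normal approximation. The t-test version gives 54.8, so 55, as stated.
- Enrolment: 111/(1 − 0.40) = 185, as stated.

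The plan gives no figure for the mechanism models, so the rest uses 54 m and n = 111 from that section plus labelled assumptions.

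**2. Share of a non-walking effect that loads on the walking slope.** Let T be arm (1:1), X walking change and Y the outcome:

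- X = δT + noise with SD s
- Y = bX + gT + error, where g is the direct (non-walking) effect of WEB

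Without T in the model, the X slope has expectation b + g × cov(X,T)/var(X) = b + g × 0.25δ/(s² + 0.25δ²). Multiplying the bias by δ puts it on the scale of the arm difference. The share of g credited to walking is 0.25d²/(1 + 0.25d²), with d = δ/s.

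The documents give no SD of 6MWT change; their 100 m is the SD of distance. The range 40 to 120 m is assumed, and s is best read as the SD after the listed adjustments.

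| SD of change (assumed) | d at 54 m | 0.25d² | Share credited to walking |
|---|---|---|---|
| 120 m | 0.450 | 0.051 | 4.8% |
| 100 m | 0.540 | 0.073 | 6.8% |
| 80 m | 0.675 | 0.114 | 10.2% |
| 60 m | 0.900 | 0.203 | 16.8% |
| 40 m | 1.350 | 0.456 | 31.3% |

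Over the same SDs, an arm difference of 27 m gives 1.2% to 10.2%, and 10 m gives at most 1.5%. With no arm difference in walking the share is zero.

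**3. False-positive rate for the walking slope.** Simulation with b = 0, n = 111, δ = 54 m, ordinary least squares, two-sided 5% level and 20,000 runs per cell. The direct effects are assumptions.

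| SD of change | Direct effect | Without arm | With arm |
|---|---|---|---|
| 100 m | 0.3 SD | 6.5% | 4.8% |
| 100 m | 0.5 SD | 10.2% | 5.0% |
| 60 m | 0.3 SD | 9.7% | 5.0% |
| 60 m | 0.5 SD | 18.6% | 4.9% |

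If WEB does not change walking, both models stay at about 5% (4.7% and 4.6% in 4,000 runs with a 0.55 SD direct effect).

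**4. Limits of the check.** It matches the linear biomarker models, where the exposure is 6MWT change. Step change enters the planned models only as a predictor of event counts. The same mechanism applies there, but the documents give no SD of step change and the size was not computed.

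**The case against.** The strongest case on the other side has five parts.

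- **Arm is not ruled out.** The covariate list is illustrative, and pooling could mean only that the association should hold in either arm. This stands as far as it goes: a reader might infer that the plan forbids arm, and it does not. But the pooling is stated and no arm term is given, while the arm comparisons name one, so an analyst following the text would probably leave it out.
- **The bias is partial.** A reader might infer that the whole of any non-walking effect is credited to walking. The algebra does not support that: the share is about 5% to 31% at 54 m, and less or nothing if the arms differ less. Controls are also urged to walk more, which could shrink the difference.
- **The contrast in content is narrower than it looks.** On WEB, the protocol says that "subjects who are current oxygen users or active smokers will receive tailored messages about oxygen use during exercise or smoking cessation". A reader might take these messages as a route unique to WEB. However, the 42-page booklet given to all subjects covers oxygen use during exercise, smoking-cessation resources and an exacerbation action plan. The clearer WEB-only routes are the online education, the community and the weekly calls.
- **The assumed direct effects are large.** A purely non-walking effect of 0.5 SD is close to the 0.55 SD total effect the plan says it can detect for secondary outcomes. This stands, and the upper false-positive rates should be read in that light.
- **Adding arm has its own weakness.** It removes the randomized part of walking change and leaves self-selected change within arms. Residual confounding by health status is then multiplied by 1 + 0.25d² (1.07 at d = 0.54, 1.25 at d = 1). In an illustration with a modest unmeasured confounder, the false-positive rate was about 15% with arm and 13% to 15% without. This is a real limit, but it does not defeat the change. With a 0.3 SD direct effect and an assumed confounder acting in the same direction, including arm lowered the rate from 25% to 15%.

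**Conclusion.** The point holds for the exploratory mechanism models. As written they can give a biased walking slope, and the section reads that slope as mechanism. The size is modest to moderate: the shares and false-positive rates above apply to the 6MWT biomarker models and rest on assumed SDs of change and assumed direct effects. The return to about 5% with arm in the model requires arm to be the only confounder. The exploratory label lowers the stakes but does not remove them, because the results are meant to inform both mechanism and future sample sizes.

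A reader might infer that the trial's efficacy conclusions are at risk. They are not: the primary and secondary arm comparisons already carry treatment and are unaffected.

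**What to change.** In Additional Analyses:

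1. Add treatment arm as a fixed covariate to every mechanism model, for biomarkers and for exacerbation and hospitalization counts.
2. Present any pooled model without arm as descriptive only.
3. Describe all results as associations, since other confounding of walking change remains after arm is included.
4. Optionally, report a walking-change-by-arm estimate with its interval. At about 111 subjects it will be imprecise and should not be used as a test.

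No new data are needed. The cost is a somewhat wider interval for the walking coefficient. With no direct effect, the standard error grows by about √(1 + 0.25d²): 4% at an SD of change of 100 m, 10% at 60 m and 21% at 40 m. The estimate will also rest on self-selected change within arms, and the report should say so.

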#### k. **Human Studies Section**

##### **(1) Risks to Subjects**

###### *1.a. Human Subjects Involvement and Characteristics:*

Collaborating Sites: VA Birmingham Medical Center (Birmingham, AL)

The majority of subjects recruited for the study will be Veterans. However, we also wish to include non-Veterans to increase the generalizability of our results and to increase our recruitment pool. We anticipate enrolling up to 185 male and female subjects with chronic obstructive pulmonary disease (COPD).

###### *Inclusion of Women and Minorities*

Both genders are eligible to participate in this study. The large male predominance in the armed services results in the fact that enrollment in any VA-based study will be disproportionately male. Only 11 % of all VA users are women. Additionally, female Veterans tend to be younger than male Veterans; since COPD prevalence increases with age, the prevalence of women with COPD in VA is expected to be lower than that for men. Accordingly, we will over recruit from the VA Boston Women's Health Clinic which provided care to 3,123 unique females in FY 12, of whom 140 had the diagnosis of COPD. All minority subjects eligible for this study will be included. To increase the diversity of our population, we will over recruit African-American Veterans. VA Birmingham is an ideal recruitment site as 21% of Veterans in Alabama are African American, and 10-15% of subjects at VA Birmingham enrolled in COPD trials are African American. Reflecting the general Veteran population, the anticipated race distribution of all subjects enrolled will be 91% White, 6.5% African American, 1.6% Native American, and 0.9% Asian. It is anticipated that 3% will be of Hispanic ethnicity.

###### *Inclusion of Children*

No children will be included in this study since we are examining adults with COPD in this project.

Inclusion Criteria are:

- a) Male and female subjects, greater than or equal to 40 years of age
- b) Clinical diagnosis of COPD defined as either a ratio of FEV1 to forced vital capacity < 0.70 or chest CT evidence of emphysema or prior documentation of FEV1/FVC ratio of < 0.7 and clinical evidence of COPD (defined as ≥ 10 pack-year cigarette smoking history, dyspnea, or on bronchodilators)
- c) Medical clearance from healthcare provider to participate in an exercise program
- d) Have access to a computer with Internet connection, a USB port or Bluetooth capability, and Windows XP/Vista/7/8/10 or higher, or Mac OSX 10.5 or higher operating system, or willing to come to VA Medical Center to use study computers
- e) Pedometer with >90% accuracy compared to manual counts on short clinic walk
- f) Competent to provide informed consent
- g) Willingness to make return visits and be available by telephone for duration of study

Exclusion Criteria are:

- a) COPD exacerbation in the previous 1 month
- b) Inability to ambulate with or without assistance
- c) Clinical signs of unstable cardiovascular disease or congestive heart failure
- d) Hypoxemia during 6MWT, i.e. oxygen saturation <85% using supplemental oxygen
- e) Inability to complete questionnaires
- f) Inability to collect at least 5 of 10 days of baseline step counts
- g) Participation in a pulmonary rehabilitation program at time of screening or within the previous 3 months
- h) Participation in another exercise-related research study at time of screening
- i) Plans to participate in an exercise-related research study in the next 12 months
- j) Plans to enroll in a supervised exercise program, such as pulmonary rehabilitation, in the next 6 months
- k) Average baseline step counts of greater than or equal to 10,000 steps per week

1.b. Sources of Materials: We expect to enroll up to 240 persons with COPD and to randomize up to 185 eligible participants. All data will be obtained specifically for research purposes. No existing specimens, records, or data will be used. Pedometer data, questionnaire data, exercise and pulmonary function data, and serum biomarker levels will be collected from human subjects and used for research purposes only.

1.c. Potential Risks. Describe the potential risks to subjects (physical, psychological, social, legal, or other) and assess their likelihood and seriousness to the subjects. Differentiate the therapeutic risk from research risk.

*Therapeutic risk* is the risk or potential risks associated with an intervention that is required for medical care, but occurs as part of the research. An example is an endoscopy that was required for medical follow-up of a specific illness.

This study has no therapeutic risks.

*Research risk* is associated with an intervention that is done only for research purposes regardless if it is an experimental intervention or a commonly used intervention, for example, an extra endoscopy. Where appropriate, describe alternative treatments and procedures, including

the risks and benefits of the alternative treatments and procedures to participants in the proposed research.

*Potential Risks:*

1.c.i. Pedometer: There is no risk to wearing the pedometer, which is commercially available. The walk performed by subjects to assess pedometer accuracy may leave subjects temporarily more short of breath. Subjects will be allowed to rest and will be allowed to use supplemental oxygen if usually prescribed.

1.c.ii. Questionnaires: The only possible risk of questionnaire administration involves the social and psychological risk resulting from inadvertent disclosure of medical history information. All questionnaire responses collected by paper and pencil will be kept confidential and locked, and identified by study code in the working databases.

1.c.iii. Physiological assessments: The pulmonary function test and 6MWT may leave a subject temporarily more short of breath. Subjects will be allowed to rest and will be allowed to use supplemental oxygen if usually prescribed. Subjects might feel lightheaded while breathing out forcefully to perform the pulmonary function test. Rarely a person might briefly pass out during the forced exhalation. Although it is unusual to have any discomfort, in those who have existing back pain, a forced exhalation may result in additional discomfort. The 6MWT may cause low oxygen levels in the blood or an irregular heart rhythm. There is a potential risk of falls during the 6MWT.

The breathing test (spirometry) is a standard pulmonary test that is commonly done. Discomforts include feeling lightheaded or short of breath while breathing out forcefully, cough or chest tightness/discomfort. Although it is unusual to have any discomfort, breathing out forcefully may cause additional discomfort if the subject has back pain before the test. The inhaler medication albuterol is given as part of this test. It is a short-acting medication that opens the airway. The most common side effects of albuterol include feeling shaky or experiencing a slight tremor or feeling heart beat slightly faster.

In pre-BD spirometry, if a participant has dyspnea triggered by spirometry, he will be allowed to use his own rescue albuterol inhaler. Once the patient recovers, spirometry will be repeated and these values will be used as the post-BD spirometry. No albuterol will be administered by the RA. In post BD spirometry, if a participant has dyspnea triggered by spirometry, a study provider will be notified to assess the patient and need for further use of BD or medical evaluation.

1.c.iv. Venipuncture: With the blood draw, a small amount of bleeding may happen under the skin causing a bruise that may last up to a week. Rarely, a blood vessel from which blood was drawn may develop a blood clot. Such a clot is not serious and requires no treatment. Also, in rare cases, fainting has occurred as a result of drawing blood. These risks are the same as those associated with a standard venipuncture performed for clinical reasons.

1.c.v. Walking exercise program: Potential physical risks related to walking and exercise include: Subjects may experience leg pain, foot pain, back pain, lightheadedness and/or dizziness with increased physical activity.

*Risks related to breathing*

Participants may experience shortness of breath while walking. This could be a sign of heart problems, but in most cases it is likely due to low fitness or the underlying lung problem.

*Risks related to musculoskeletal injury or falls*

Walking exercise programs are less likely than more vigorous exercise programs to result in minor musculoskeletal injury. However, musculoskeletal injury and falls can occur in walking programs.

*Risks related to cardiovascular disease*

Some of the participants in this study will have cardiovascular disease risk factors, and thus they are at increased risk of experiencing an adverse cardiovascular event such as angina or a myocardial infarct.

*Risks related to chronic pain*

Regular exercise, such as walking, is generally recommended for people with chronic pain. However, when starting a walking program, individuals with chronic pain may experience temporary muscle soreness or stiffness. A walking program may worsen an underlying pain condition.

*Risks related to diabetes*

Some of the participants in this study will have diabetes. An exercise program is an important part of managing diabetes. However, there are some risks, such as low blood sugar episodes after exercising or problems with ulcers or sores on the feet.

*Risks related to blood pressure control*

Starting an exercise program may lower an individual's blood pressure. Participants who take medication to lower their blood pressure may need to have their blood pressure medication adjusted as they progress in the program. Likewise, participants who have poorly controlled blood pressure may experience raised blood pressure as they progress in the program.

*Risks related to hydration*

Participants who are on fluid restriction or diuretics may have trouble hydrating sufficiently when walking in hot weather.

1.c.vi. Psychological Risks:

The content of questionnaires and the study website are on topics not generally considered controversial or likely to produce psychological distress.

1.c.vii. Social and Economic Risks:

There is the potential for loss of confidentiality with the use of the Internet.

*Website and Server.* The website is password protected and secured. The server is on secured networks within the University of Michigan firewalls.

We use many procedures to protect the research database but despite these measures, there is a chance that a person not connected with the study may gain access to the website information. No protected health information (PHI) will be stored on the study server. The UMich server does not track IP addresses.

Only the following information, all of which are not identifying, will be stored on the server:

- Unique study ID
- Password and username
- Step count numbers from pedometer

1.c.viii. Measures of body composition and bone mineral density by DXA Scan (VABoston site only): There is a slight amount of radiation from having a bone density scan but this is less than one-tenth of the amount one would receive from having a chest x-ray and unlikely to result

in any illness from the radiation exposure. Due to the use of radiation in the DXA scan, this test will not be performed if a participant is pregnant or nursing since there may be risks that are not foreseeable. Women of childbearing potential enrolling in this study must (i) have been using a contraceptive measure (an intrauterine device (IUD), oral contraceptives, barrier methods, or abstinence) for the previous three months, (ii) must have a negative pregnancy test, and (iii) must agree to continue to use a contraception measure for the duration of the study. Women are considered to be of childbearing potential unless they have been surgically sterilized or are post-menopausal, that is, no menstrual period for more than 6 months. Nursing mothers may not participate in this study. Participants will be provided the results of their scans done at the standard sites (total hip, femoral neck radius) and told if they meet standard diagnostic criteria for osteopenia or osteoporosis. A report will be prepared that they will be asked to give to their usual healthcare provider. Any female participant who self-reports pregnancy or has a positive pregnancy test at any study visit will not perform the DXA scan and will have the option to discontinue participation in the research study.

1.c.ix. Measure of body composition using bioimpedance (VA Boston site only): To measure body fat levels using the Omron Healthcare Fat Loss Monitor (HBF-306CN), a painless, extremely low level of electrical current (50 kHz and 500  $\mu$ A) is used. Subjects who are pregnant are excluded from the DXA Scan and are therefore, also excluded from the bioimpedance measurement. Although likely safe for use in those with implanted medical devices, we will exclude any subject with a pacemaker or defibrillator to minimize any potential risks. Before completing this assessment, the study staff will complete a safety screening that includes:

- Asking if s/he has a pacemaker and or defibrillator
- Requesting the subject empty the bladder beforehand

If the subject has a pacemaker or defibrillator, then the bioimpedance measurement will not be taken. The bioimpedance measurement is safe and painless, and is taken while the subject is seated. The subject will grasp 2 handles on the fat loss monitor for 5-10 seconds in the seated position while a reading is taken. Three readings will be taken in this manner to assess reproducibility.

